adherence to match data published after SAP draf (Section 5). Required subgroup analy have at least 10 observat per treatment arm for ana (Section 7). Updated diplopia tabulat to match case report form (Section 8).	must or sitivity cipants ace of 2 stage on 3). sensor fted syses to tions alysis tions m	Clarified criteria for sensitival analysis excluding participate with interocular difference of lines (Section 2). Clarified that the false discovery rate will be controlled for secondary outcomes using the two-stag step-up procedure (Section 3). Edited threshold for exploratory temperature sense adherence to match data published after SAP drafted (Section 5). Required subgroup analyses have at least 10 observations per treatment arm for analys (Section 7). Updated diplopia tabulations to match case report form	06May2025	[name]			1.2

Signature Page

Signature of Author: [name] [name]

I agree to the terms defined by the placement of my

document signature in this document

2025-05-06 11:29-04:00 Signature in this docume 2025-06-02 08:21-04:00

Signature of Approver:

[name]

I agree to the terms defined by the placement of my signature in this

document

2025-05-06 11:22-04:00

1 Purpose of IXT7 Study

The objective of the IXT5 study is to determine whether 3 months of full-time patching is more effective than observation for improving distance control of IXT (on-treatment outcome). A total of 72 participants will be randomly (1:1) assigned to the following treatment groups:

• Observation for 3 months – no treatment other than refractive correction

Full-time (FT) patching (all waking hours) for 3 months (right eye on even days, left eye on odd days), in addition to refractive correction

2 Primary Analysis – Efficacy of Full-Time Patching (3 Months, On-Treatment)

The primary outcome is change from baseline to 3 months in mean (of 3 measurements) distance control score (mean 3-month score – mean baseline score). Single control scores are integer-valued and range from 0 to 5 with 0 indicating no deviation (no tropia or phoria) and 5 indicating constant tropia. To meet eligibility criteria, the mean score must be ≥ 2.0 and ≤ 5.0 points. Hence, the change in mean control score is a quasi-continuous, bounded measurement with possible values ranging from -5.0 to 3.0 points, with negative values indicating improvement and positive values indicating worsening.

The primary analysis will be a two-sided comparison of the mean change in 3-month control of the distance exodeviation between the treatment groups using an analysis of covariance (ANCOVA) model which adjusts for the baseline distance control and distance PACT (prism and alternate cover test) angle. The

21 ANCOVA model will test the hypothesis that the treatment effect is different from zero (superiority

hypothesis) using a type I error rate of 5%. An adjusted treatment group difference (FT patching –
 Observation) and corresponding 95% confidence interval and p-value will be estimated from the ANCOVA

24 model.

2.1 Principles to be Followed in Primary Analysis

Model assumptions for ANCOVA will be assessed, including linearity of the adjustment covariates (baseline distance control and distance PACT angle), normal distribution of the outcome, and equal variance in the treatment groups. The linearity assumption of the baseline covariates will be evaluated using scatterplots and by categorizing each of the baseline factors in the ANCOVA model to check for approximate linearity of the coefficients across the ordered categories. Each baseline covariate will be included as a continuous covariate in the model if the assumptions for linearity are met for that covariate; otherwise, the baseline covariate will be categorized.

When three measures of distance control are not performed at the outcome exam, the mean of two measurements, or failing that, a single measurement, will be used if available.

The primary analysis will follow the intention-to-treat principle, with all participants analyzed according to their randomized treatment group, with the following stipulations:

• For participants who receive non-randomized treatment between baseline and 3 months, the distance control score data from the early 3-month visit will be used for the primary outcome. Early outcome visits are not required to fall within the 3-month visit window to be included in analyses.

• Participants who miss the 3-month visit or do not complete any control testing at the 3-month visit, and who do not have an early 3-month outcome visit, will have their mean distance control score imputed using multiple imputation.

• For all participants other than above, to be included in the analysis, the 3-month visit must be completed within the analysis window defined as 46 to 137 days from randomization; otherwise, the distance control at the 3-month visit will be imputed using multiple imputation.

 The multiple imputation for missing data will be performed using Monte Carlo Markov Chain (MCMC) model. (See Section 2.3 below for further details.)

2.2 Sensitivity Analyses

Sensitivity analyses of the primary outcome will repeat the primary analysis with the following modifications:

2.2.1 Sensitivity Analysis #1: Tipping Point Analysis to Test the Missing at Random Assumption of the Primary Analysis

MCMC multiple imputation assumes that missing data are missing at random (MAR). To test this assumption, a tipping point analysis will be performed. In IXT7, the MAR assumptions means that whether the 3-month control score is missing or observed may be a function of the baseline PACT angle and baseline control score, which are included in the imputation and analysis models, but are not a function of the missing data being imputed, after conditioning on the baseline control and PACT angle. This assumption cannot be tested directly as missing data are unknown. The tipping point analysis will adjust the imputed values using a shift parameter to determine how severe the departure from MAR must be to change the conclusion of the analysis with respect to rejecting or failing to reject the null hypothesis.

If the 3-month outcome in one group is significantly better than the other (significantly lower mean control score as determined in the primary analysis), a shift parameter will be applied to the imputed values in that group to determine the tipping point at which the results of the primary analysis are nullified. That is, if one group is found to be superior ($P \le .05$), the tipping point will identify the shift parameter necessary to yield P > .05. Conversely, if the null hypothesis is not rejected (P > .05), two tipping points will be identified – one that would make patching group superior and one that would make observation group superior. In either case, this tipping point will be evaluated to determine if it is plausible, or even possible given the control score range is bounded. If not possible, the MAR assumption does not affect results, regardless of plausibility. If possible but not plausible, the MAR assumption is likely reasonable. If plausible, the sensitivity of study results to missing data will be reported as a potential study weakness.

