864 of 1.8 points (95% CI, 1.4 to 2.5 points) after 8 weeks. Therefore, we estimate that a mean
865 change of 1.45 points after 3 months of full-time patching in the current study is reasonable for
866 an active treatment.

867 **Sample Size Estimation:**

868 The study will be powered for the primary objective.

869 Assuming a mean change in distance control score after 3 months of 0.30 points in the
870 observation group and 1.45 points in the full-time patching group; we estimate that the true
871 difference is 1.15 points between full-time patching and observation at 3 months.

872

873 **Hypothesis Test for Objective – FT vs OBS at 3 Months:**

874 Assuming a pooled standard deviation of 1.5 points for change in distance control score after 3
 875 months, and a correlation of 0.30 between distance control score at baseline and change from
 876 baseline after 3 months, a total sample size of 68 participants (34 per group) completing the 3-
 877 month outcome has 90% power with a type I error rate of 5% to evaluate whether there is a
 878 treatment group difference between FT patching and OBS if the true difference is 1.15 points,
 879 Table 2. Accounting for 5% loss to follow-up after 3 months, a total of 72 participants (36 per
 880 treatment group) will need to be enrolled. The overall number of participants with an interocular
 881 difference in distance VA of 2 logMAR lines (10 letters on E-ETDRS for patients ≥ 7 years old) will be
 882 limited to 14.

883 **Table 2: Total Sample Size for Difference in Mean Distance Control Score**

Standard Deviation of Change in Distance Control (points)	Treatment Group Difference for Outcome of Mean Change in Distance Control (points)		
	0.85	1.00	1.15
1.4	106	78	60
1.5	122	90	68
1.6	138	100	78

884 Cells indicate N for the overall study (two treatment groups combined with a ratio of 1:1), using a 2-sided test with
 885 alpha 0.05, from an analysis of covariance model evaluating a difference between treatment groups for mean change
 886 from baseline in distance control, controlling for baseline distance control.

887

888 If the true effect with FT patching is as small as 0.99, the study would still have 80% power to
 889 reject the null in favor of a difference (and 1.05 with 85%).

890 **7.4 Interim Monitoring**

891 Given the short duration of the primary outcome at 3 months, there will be no formal interim
 892 analysis for stopping the study early for efficacy or futility.

893 **7.5 Analysis Datasets**

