2.3 Multiple Imputation of Missing Values

The multiple imputation will be performed for missing data using Monte Carlo Markov Chain (MCMC) modeling, which includes the mean distance control score at baseline and the change in mean distance control score from baseline to the 3-month (or early outcome) visit, and the distance PACT at baseline. Imputed values will be limited to the range of possible changes in mean control score (-5.0 to 3.0), using options available in the imputation software. If necessary, observed 3-month control scores may be transformed to achieve (or approximate) the normal distribution prior to imputing, and then backtransformed for analysis.

- The multiple imputation will be performed separately by treatment group to account for potential
- interaction between the treatment groups and the follow-up distance control scores. The number of
- imputations will be set to 100. Missing baseline data are not expected for distance PACT angle; however, if
- such missing data occurs, it will be imputed in the MCMC model so that participants with missing baseline
- data are included in the analysis.

3 Secondary Analyses

- All secondary analyses described below will use observed data only without imputation for missing data.
- Only data from 3-month outcome visits that occurred within the analysis window (or data from early 3-
- month outcome visits) will be included in analysis. For all secondary outcomes, the data will be tabulated,
- and means and standard deviations, or numbers with the outcome and percentages, will be calculated for
- each of the treatment groups. The false discovery rate will be controlled at 5% using the two-stage step-up
- procedure¹ to account for multiple secondary outcomes. Reported p-values and confidence intervals will
- incorporate the FDR adjustment.

120121

112

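### The tipping-point analysis shifts only the better group's imputed scores, so an impossible tipping point does not show that MAR has no effect on the result

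*SAP*

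**What the plan says.** SAP 2.2.1 (Sensitivity Analysis #1) deals with a significant primary result as follows: "a shift parameter will be applied to the imputed values in that group to determine the tipping point" at which significance is lost. The group meant is the one with the better outcome. The tipping point is then sorted into one of three classes. If it is plausible, sensitivity to missing data is reported as a potential weakness. If it is possible but not plausible, MAR is called likely reasonable. For a tipping point outside the bounded scale the SAP says: "If not possible, the MAR assumption does not affect results, regardless of plausibility".

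If the primary result is not significant, "two tipping points will be identified", one in favour of each group. The arm to be shifted is not named.

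On the imputation itself, SAP 2.3 says: "The multiple imputation will be performed separately by treatment group to account for potential" interaction. Under SAP 2.1, a score is imputed when the 3-month visit is missed, lacks control testing, or falls outside days 46 to 137, in either arm. For participants who start non-randomized treatment, "control score data from the early 3-month visit will be used for the primary outcome", which removes some informative missingness but not all of it.

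**The concern.** The sentence is about MAR as a whole, but the analysis behind it varies MAR in one arm. The estimated difference uses imputed scores from both arms, each drawn from its own model under its own MAR assumption. An impossible shift in the better arm shows that departures in that arm alone cannot change the conclusion. It says nothing about departures in the other arm, or in both together.

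The clearest case is when every missing score is in the other arm. There is nothing to shift and no tipping point exists, so, read literally, only the strongest class applies although no departure has been examined. The SAP does not address this case.

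Nothing else fills the gap. SAP sensitivity analyses #2 and #3 drop imputed scores, #4 excludes participants with a 2-line interocular difference, and Protocol 7.6.1 lists two complete-case analyses and the same exclusion. A significant result could therefore be reported as immune to missing data when departures inside the scale would overturn it.

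**Working it through.** **Inputs from the documents.** SD of change 1.5, correlation with baseline 0.30, difference 1.15, 36 per arm enrolled and 5% loss (Protocol 7.3); two-sided alpha 0.05 and ANCOVA on baseline control and PACT (SAP 2); scale 0 to 5. The 3-month observation mean is taken as 2.6 (2.59 in Protocol Table 1).

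**The plan's own figure.** Residual SD s = 1.5 × √(1 − 0.30²) = 1.431. The noncentral t with 34 per arm (65 df) gives 90.4% power at 1.15. That agrees with the stated 68 completers, and 68/0.95 = 71.6, rounded up to 72 enrolled.

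**Two limits on the observed difference d**, with k scores missing per arm, patching mean mP = 2.6 − d, and t(0.975, 68) = 1.995:

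- *SAP rule* (patching's k imputed scores all at 5): significance is just lost when d − (k/36)(5 − mP) = t·√(vP/36 + s²/(36 − k)), where vP = [(35 − k)s² + (36 − k)(k/36)(5 − mP)²]/35.
- *Both arms* (observation's k imputed scores also at 0): d − (k/36)(5 − mP) − (k/36)(2.6) = t·√((vP + vO)/36), where vO is vP with 2.6 in place of 5 − mP.

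Between the two limits, the SAP declares the tipping point impossible although shifts inside the scale remove significance.

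**Worked case: k = 2, d = 1.00, s² = 2.0475.**

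- Primary: SE = 1.431 × √(2/34) = 0.347, p = 0.005.
- Patching at 5: 1.00 − (2/36)(3.4) = 0.811; vP = 2.554; SE = 0.362; t × SE = 0.723. The difference stays significant (p = 0.028), so the SAP's answer is that MAR has no effect.
- Observation also at 0: 0.811 − (2/36)(2.6) = 0.667; vO = 2.295; SE = 0.367; t × SE = 0.732. Significance is lost (p = 0.074).

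**Solved limits.**

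| Missing scores | Differences wrongly certified |
|---|---|
| 2 per arm (2/36 = 5.6%) | 0.90 to 1.07 (primary p 0.011 to 0.003) |
| 3 per arm (8.3%) | 1.03 to 1.29 |
| 4 per arm (11.1%) | 1.17 to 1.53 |
| 2 in observation only | 0.68 to 0.84 |
| 3 in observation only | 0.69 to 0.92 |
| 4 in patching only | none (both limits 1.148) |

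Moving the observation mean over its Table 1 interval (2.35 to 2.82) changes the per-arm lower limits by at most about 0.05 and the upper limits by about 0.01.

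**Simulation check** (imputation by arm, Rubin's rules, scores held to 0 to 5, latent true difference 1.15). In 400 trials per case, ANCOVA adjusted for baseline control only. Among significant trials with an impossible one-arm tipping point, moving both arms to their bounds removed significance in 82 of 297 (2 missing per arm), 105 of 215 (3 per arm), 137 of 180 (4 per arm), 74 of 352 (3 in observation only) and 0 of 180 (4 in patching only). A smaller run (60 trials per setting, 30 imputations, PACT added with an assumed mean of 25 and SD of 7) had 56 significant trials with 2 missing per arm. Of these, 7 tipped with the better arm alone, 17 only with both arms, and 32 not at all. All these counts are illustrative and measure what is possible, not what is plausible.

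**The case against.** The strongest reply is that the shifts needed are extreme. Move the arms one residual SD each in opposite directions. Ignoring the added variance, significance is lost only if d is below (2k/36)(1.431) + t × 1.431 × √(2/(36 − k)), which is 0.85, 0.94 and 1.03 for k = 2, 3 and 4. Each value lies at or below the start of the corresponding range. At that start, the two opposing shifts must total roughly 3.8 to 4.1 points on a 5-point scale. At the upper end, every missing patched child scores 5 and every missing observed child 0, while Protocol 1.9.2 puts spontaneous resolution at about 7% over 3 years. Correcting the rule would often change the label only to the SAP's middle class.

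That is fair on practical weight, but it does not rescue the sentence. The SAP puts these results in the class where plausibility is expressly not considered, so the judgement the objection relies on is never made.

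Two further points stand. At the planned loss, 1.15 lies above the range. And the roughly 11% loss in Table 1 (16/147 = 10.9%, 15/131 = 11.5%) is a weak benchmark for the 4-per-arm case: 3 months was an intermediate visit in that trial, whereas here it is the final one and the SAP accepts a wide window and early visits.

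Shifting only the winning arm is also a reasonable stress test in itself. The fault is the general conclusion drawn from it.

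**Conclusion.** The concern holds. As written, the rule can certify a significant result as independent of MAR when departures within the scale would make it non-significant. The rule is correct only when all missing scores are in the better arm.

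The size depends on how many scores are missing and in which arm, which the documents do not give by arm. Protocol 7.3 plans only the total ("Accounting for 5% loss to follow-up after 3 months"), about 4 of 72. An even split gives a range about 0.17 points wide (1.072 − 0.904 = 0.168). The range first contains 1.15 at 3 missing per arm. Observation-only missingness affects smaller differences, where more modest shifts are enough.

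The primary estimate, test and sample size are untouched. This should be corrected because it governs how robust the main result will be said to be. The unnamed arm for P > .05 is a separate and lesser omission.

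**What to change.** In SAP 2.2.1, apply a separate shift parameter to each arm over a two-way grid, with shifted scores held to 0 to 5, for significant and non-significant results alike. Report the combinations that change the conclusion. State that MAR does not affect the result only if no combination within the scale does so, and judge the rest by the SAP's existing plausibility classes.

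The minimum alternative is to limit the sentence to departures in the shifted arm and to name the arm shifted when P > .05.

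The grid reuses the same 100 imputations, needs no new data and adds little analysis work; the minimum version is a wording change. The one drawback is that the result may look slightly less robust.

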2.2.2 Sensitivity Analysis #2: Complete Case Analysis (Excluding Imputed Control Scores)

Participants whose 3-month control score was imputed in the primary analysis will be excluded from the analysis.

2.2.3 Sensitivity Analysis #3: Complete Case Analysis (Excluding Imputed Control Scores and Early Outcome Visits)

Repeat the sensitivity analysis in section 2.2.2 excluding data from participants who completed an early outcome visit.

2.2.4 Sensitivity Analysis #4: ITT Excluding Participants with IOD 2 LogMAR Lines at Enrollment

The primary analysis will be repeated excluding participants of any age with IOD of 2 logMAR lines (8 or more letters for E-ETDRS and 2 logMAR lines for ATS-HOTV).

2.3 Multiple Imputation of Missing Values

The multiple imputation will be performed for missing data using Monte Carlo Markov Chain (MCMC) modeling, which includes the mean distance control score at baseline and the change in mean distance control score from baseline to the 3-month (or early outcome) visit, and the distance PACT at baseline. Imputed values will be limited to the range of possible changes in mean control score (-5.0 to 3.0), using options available in the imputation software. If necessary, observed 3-month control scores may be transformed to achieve (or approximate) the normal distribution prior to imputing, and then backtransformed for analysis.

- The multiple imputation will be performed separately by treatment group to account for potential
- interaction between the treatment groups and the follow-up distance control scores. The number of
- imputations will be set to 100. Missing baseline data are not expected for distance PACT angle; however, if
- such missing data occurs, it will be imputed in the MCMC model so that participants with missing baseline
- data are included in the analysis.

3 Secondary Analyses

- All secondary analyses described below will use observed data only without imputation for missing data.
- Only data from 3-month outcome visits that occurred within the analysis window (or data from early 3-
- month outcome visits) will be included in analysis. For all secondary outcomes, the data will be tabulated,
- and means and standard deviations, or numbers with the outcome and percentages, will be calculated for
- each of the treatment groups. The false discovery rate will be controlled at 5% using the two-stage step-up
- procedure¹ to account for multiple secondary outcomes. Reported p-values and confidence intervals will
- incorporate the FDR adjustment.

120121

112

3.1 Near Control

- At 3 months, change in near control (mean of 3 measurements) will be evaluated similarly to distance
- control in the primary analysis using an ANCOVA model that adjusts for the mean near control score at
- baseline and the near angle by PACT at baseline. If only 2, or 1, near control measurements are available,
- the 3-month near control score will be calculated based on the available measurements, as will the change
- from baseline.

127

- Additionally, the proportion of participants with 2 or more points improvement from baseline in mean near
- control will be tabulated and compared between the treatment groups at 3 months using a two-sided
- Barnard's test, separately for distance and near. The treatment group difference and 95% confidence
- interval will be estimated by inverting Barnard's test, using the method of Agresti and Min.²

132133

3.2 Angle of Deviation

- 134 At 3 months, the angle of deviation by PACT will be described using mean, SD, and range, and compared
- between treatment groups using an ANCOVA model, adjusting for baseline PACT angle. The analysis will
- be completed separately for the distance and near angles. Esodeviations will be represented using a
- negative sign to differentiate them from exodeviation.

138 139

- Additionally, the proportions of participants with improvement of distance angle and improvement of near
- angle (separately) at 3 months greater than the test/retest variability will be compared between the
- treatment groups using Barnard's test. The treatment group difference and 95% confidence interval will be
- estimated by inverting Barnard's test, using the method of Agresti and Min.² The published test-retest
- 143 criteria³ are as follows:

144 145

146

147

149

At distance:

- If deviation magnitude $\leq 20 \Delta$, $\geq 4 \Delta$ decrease exceeds test-retest variability
- If deviation magnitude $\geq 20 \Delta, \geq 8 \Delta$ decrease exceeds test-retest variability

148 At near:

- If deviation magnitude $\leq 20 \Delta$, $\geq 7 \Delta$ decrease exceeds test-retest variability
- If deviation magnitude >20 Δ , \geq 13 Δ decrease exceeds test-retest variability

150 151

- Development of an esodeviation ≥ 4 Δ will not be counted as an "improvement in angle" in these analyses.
- Also, although the same guidelines above apply to classifying increases in angle as beyond test-retest
- variability, only decreases in angle are of interest here.

155156

